### **3.8.3. Adverse Events of Special Interest**

Adverse events of special interest (AESI) of tovorafenib will be summarized as below based on TEAEs:

- Rhabdomyolysis, based on the SMQ “Rhabdomyolysis”, narrow scope terms
- Ventricular Arrhythmias, based on SMQ “Ventricular tachyarrhythmias”
- Intra-tumoral hemorrhage, based on SMQ “Haemorrhagic central nervous system vascular conditions” and PT Tumour Haemorrhage
- Secondary primary malignancies, based on SMQ “Non-haematological malignant tumours”
- Ocular toxicity, based on MedDRA SOC “Eye disorders”, excluding HLG Ts “Congenital eye disorders (excl glaucoma)”, “Ocular neuromuscular disorders”, and “Ocular neoplasms”
- Decreased growth velocity, based on PT “Growth disorder”, “Growth failure”, “Growth retardation”, “Body height decreased”, “Body height abnormal”, “Short Stature”.

The AESIs will be summarized by group term, PT and highest CTCAE grade.

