Non-serious adverse events of special interest should be reported by the Investigator to the Sponsor immediately (ie, no more than 24 hours after learning of the event; see Section [8.1.4](#) for reporting instructions).

Adverse events of special interest for this study include the following:

1. Rhabdomyolysis
2. Ventricular Arrhythmias
3. Intra-tumoral hemorrhages
4. Secondary primary malignancies
5. Ocular toxicities

Events NOT Meeting the AE Definition

- Any clinically significant abnormal laboratory findings or other abnormal safety assessments that are associated with the underlying disease, unless judged by the Investigator to be more severe than expected for the patient's condition
- The disease/disorder being studied or expected progression, signs, or symptoms of the disease/disorder being studied, unless more severe than expected for the patient's condition
- Interventions for pretreatment conditions (e.g., elective cosmetic surgery) or medical procedures that were planned before study participation (e.g., port placement)
- Unplanned medical or surgical procedures (e.g., endoscopy, appendectomy). The condition that leads to the procedure is the AE
- Situations in which an untoward medical occurrence did not occur (social, logistical, and/or convenience admission to a hospital)
- Anticipated day-to-day fluctuations of preexisting disease(s) or condition(s) present or detected at the start of the study that do not worsen

Definition of SAE

If an event is not an AE per definition above, then it cannot be an SAE, even if serious conditions are met (e.g., hospitalization for signs/symptoms of the disease under study, death due to progression of disease).

An SAE is defined as any untoward medical occurrence that, at any dose:

a. Results in death

b. Is life-threatening

The term “life-threatening” in the definition of “serious” refers to an event in which the patient was at risk of death at the time of the event. It does not refer to an event that hypothetically might have caused death, if it were more severe.

c. Requires inpatient hospitalization or prolongation of existing hospitalization

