- The Investigator will also consult the Investigator's Brochure (IB) and/or Product Information for marketed products in his/her assessment.
- For each AE/SAE, the Investigator must document in the medical notes that he/she has reviewed the AE/SAE and has provided an assessment of causality.
- There may be situations in which an SAE has occurred, and the Investigator has minimal information to include in the initial report to the Sponsor's Drug Safety Group. **However, it is very important that the Investigator always make an assessment of causality for every event before the initial transmission of the SAE data to the Sponsor's Drug Safety Group or designees.**
- The Investigator may change his/her opinion of causality in light of follow-up information and send an SAE follow-up report with the updated causality assessment.
- The causality assessment is one of the criteria used when Sponsor determines regulatory reporting.

Follow-up of AEs, AESIs, and SAEs

- The Investigator is obligated to perform or arrange for the conduct of supplemental measurements and/or evaluations as medically indicated or as requested by the Sponsor's Drug Safety Group or designee to elucidate the nature and/or causality of the AE or SAE as fully as possible. This may include additional laboratory tests or investigations, histopathological examinations, or consultation with other health-care professionals.
- If a patient dies during participation in the study or during a recognized follow-up period, the Investigator will provide the Sponsor with a copy of any postmortem findings, including histopathology, as applicable.
- The Investigator will submit any updated SAE data to Sponsor within 24 hours of receipt of the information, and should submit follow-up on non-serious AESIs in a similar manner.

Reporting of SAEs and AESIs (serious and non-serious)

SAE/AESI Reporting to Sponsor via the SAE Report and AESI Targeted Questionnaire Forms

The Investigator is responsible for ensuring that AEs are monitored and reported. See Section 8.1.1 for greater details regarding the AE, AESI, and SAE reporting periods.

- Report SAEs and non-serious AESIs by completing the paper SAE form (see next section) in order to report the event within 24 hours.
- For all AESIs (serious and non-serious), the applicable AESI targeted questionnaire form should be submitted with the SAE form or as soon as possible
- Contacts for SAE reporting can be found in the Study Manual.

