## **1. INTRODUCTION**

DAY101-102a is a Phase 2, multi-center, open-label sub-study of tovotafenib (DAY101) as a monotherapy in patients  $\geq 12$  years of age with recurrent or progressive melanoma or solid tumors with activating BRAF fusion or CRAF/RAF1 fusions or amplification.

The statistical analysis plan (SAP) contains a detailed description of the data presentations and statistical analyses that will be included in the clinical study report for Protocol DAY101-102a. The statistical methods and analyses described here are based on those presented in the Study DAY101-102 Master Protocol Amendment 2 (dated 13 October 2022) and Study DAY101-102a Monotherapy Subprotocol Amendment 2 (dated 19 October 2022).

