### **3.2.4. Subgroup Analyses**

Due to the small sample size, subgroup analyses of key efficacy endpoints will only be performed for the following baseline variables:

- Sex (Female, Male)
- CNS tumor (Yes, No; tissue agnostic cohort)

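### SAP 3.8.3 counts intra-tumoral hemorrhage by a MedDRA search without the investigator-reported AESIs, so the row can include CNS bleeds unrelated to a tumour and omit reported extracranial tumour bleeds

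*SAP*

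**What the plan says.** Protocol Appendix G lists "Intra-tumoral hemorrhages" among the AESIs and attaches no anatomical restriction. Protocol 8.1.1 and Appendix G require a non-serious AESI to be reported to the sponsor as an SAE is, within 24 hours. For serious and non-serious AESIs alike, Appendix G adds that "the applicable AESI targeted questionnaire form should be submitted with the SAE form" or as soon as possible.

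SAP 3.8.3 takes another route. AESIs "will be summarized as below based on TEAEs", and each is identified by MedDRA terms. For intra-tumoral hemorrhage the terms are the SMQ "Haemorrhagic central nervous system vascular conditions" and the "PT Tumour Haemorrhage". On presentation it says: "The AESIs will be summarized by group term, PT and highest CTCAE grade".

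SAP 1 describes the population as patients with "recurrent or progressive melanoma or solid tumors with activating BRAF fusion or CRAF/RAF1 fusions or amplification". Among the subgroups in SAP 3.2.4 is "CNS tumor (Yes, No; tissue agnostic cohort", so patients without a CNS tumour are expected.

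**The concern.** The label and the search describe different things. The label means bleeding into a tumour, wherever the tumour is. Judged by its title, the SMQ selects bleeding by site (the CNS) and does not ask whether a tumour is there. Outside the CNS, a single PT has to catch every tumour bleed.

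The sponsor should already hold the information that would settle each case, because the protocol requires sites to report this event and complete a questionnaire on it. The SAP does not use it. The count for a bleeding risk that the sponsor chose to monitor specially could then disagree with the sponsor's own AESI reports, and no planned output would show or explain the difference.

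**Working it through.** No arithmetic applies: the plan gives no figure for this event. The check is to apply the SAP search, as written, to the kinds of bleed that the enrolled population could have.

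**Inputs.** The AESI term and the reporting rules come from Protocol 8.1.1 and Appendix G. The search, its data source and its presentation come from SAP 3.8.3. The other AE outputs come from SAP 3.8.1 and 3.8.2, and the population from SAP 1, 2.2 and 3.2.4. The SMQ's term list is not in the documents, so its content is read from its title.

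| Event | Coded to | In the SAP row? | Matches the label? |
|---|---|---|---|
| Bleed into a CNS tumour | a term in the SMQ, or Tumour Haemorrhage | Yes | Yes |
| CNS bleed, no tumour at that site | a term in the SMQ | Yes | No |
| Bleed into an extracranial tumour | Tumour Haemorrhage | Yes | Yes |
| Bleed into an extracranial tumour | another PT, such as an organ-bleeding term outside the SMQ | No | No |

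The second and fourth lines are the two errors. Neither is corrected elsewhere in 3.8.3, for these reasons:

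1. No condition requires a tumour at the bleeding site, so the second line is counted.
2. No investigator AESI report or questionnaire is used to include an event, so the fourth line is omitted even when the site reported it as this AESI.
3. The scope of this SMQ (narrow or broad) is not stated, although 3.8.3 does specify narrow scope for rhabdomyolysis. The search is therefore not fully defined.

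**What the other outputs show.** SAP 3.8.1 lists all AEs, and SAP 3.8.2 tabulates TEAEs by SOC and/or PT and grade. A treatment-emergent bleed on the fourth line appears in both. However, 3.8.1 names no AESI listing, and neither section mentions an AESI identifier. A reader could not tell from these outputs which haemorrhages were reported as intra-tumoral.

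**Size.** The documents give no bleeding rate, no split of coding between PTs and no SMQ term list, and the cohort sizes are redacted. The number of misclassified events cannot be derived. All that follows is the effect of one such patient on a percentage, which is 100/N points. SAP 3.2.4 says only that the sample is small. If N were 20 to 40 (an assumption, for illustration), one patient would move the figure by 100/20 = 5 to 100/40 = 2.5 percentage points.

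**The case against.** The strongest case for the SAP is that a term search fixed in advance is reproducible and a legitimate choice. Section 3.8.3 uses one for all six of its AESIs, and reliance on investigator reports carries its own risk of under-reporting. That stands, and it is why the search should be kept and not replaced.

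A reader might infer that extracranial tumour bleeds are missed altogether. The documents do not support this. Tumour Haemorrhage names no site, so a bleed coded to it is counted wherever it occurs. Appendix G also asks investigators to record a diagnosis in preference to signs and symptoms where possible, which makes that coding more likely when the site believes the bleed is in the tumour. Only bleeds coded to another PT drop out, and nothing shows how often that would happen.

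A reader might also infer that safety data are lost. They are not: the events stay in the AE listings and, when treatment-emergent, in the TEAE tables. Because the AESI table is also shown by PT, a CNS haemorrhage term is visible as such under the group term. The group total still carries the wrong label, and the omitted events are still absent from it.

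Finally, the study was stopped early, the AESI output is descriptive, and no decision rule depends on this rate. That limits the consequence. It does not make the row count what it names.

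**Conclusion.** The point holds in a limited form. As written, the SAP's intra-tumoral hemorrhage group can include CNS bleeds unrelated to any tumour. It can also omit extracranial tumour bleeds coded to a PT other than Tumour Haemorrhage, even when the site reported them as this AESI. Both are possibilities that the definition leaves open, not errors shown to have occurred. The fault is confined to the AESI count, and any stated percentage of over- or under-counting would have no basis in the documents.

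The conclusion assumes that the SMQ contains what its title says and that organ-bleeding terms outside the CNS are not in it. It also assumes that the DAY101-102a sub-protocol and the questionnaire, neither of which is among the documents, do not restrict the AESI to CNS tumours. No efficacy endpoint is affected. A named safety count is, and the remedy is cheap enough that the change should be made.

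**What to change.** In SAP 3.8.3:

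- Add a row, with a by-patient listing, of intra-tumoral hemorrhages that the investigator reported as AESIs, taken from the SAE form or the targeted questionnaire.
- Keep the present MedDRA search as a separate row. Label its SMQ component as CNS haemorrhage and state whether the narrow or broad scope is used.
- List every event that is in one set and not in the other.

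The cost is a small reconciliation of the AESI reports with the AE data before database lock, and two rows where there was one. Appendix G describes paper SAE forms, and the documents show no AESI flag in the eCRF, so the matching may have to be done by hand. The reports themselves are already required by the protocol, so no new data collection is needed.

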8.1.6. Death Events

Deaths occurring during the AE reporting period, regardless of attribution to DAY101 or combination partner will be recorded as a serious AE and expeditiously reported to the Sponsor. This includes death attributed to the progression of malignant disease.

When recording a death, the event or condition that caused or contributed to the fatal outcome should be recorded as the single medical condition on the Adverse Event eCRF and SAE report form, as applicable. If the cause of death is unknown and cannot be ascertained at the time of reporting, then “unexplained death” should be recorded on the Adverse Event eCRF and SAE reporting form, as applicable.

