
• Any abnormal laboratory test results (hematology, clinical chemistry, or urinalysis) or other safety assessments (e.g., electrocardiogram [ECG], radiological scans, vital signs measurements), including those that worsen from baseline, considered clinically significant in the medical and scientific judgment of the Investigator (i.e., not related to progression of underlying disease). In general, abnormal laboratory findings without clinical significance (based on the Investigator's judgment) are not to be recorded as AEs. However, abnormal laboratory findings that result in new or worsening clinical sequelae, require therapy, or adjustment in current therapy are considered AEs. Where applicable, clinical sequelae (not the laboratory abnormality) are to be recorded as the AE. If the clinically significant laboratory abnormality is a sign of a disease or syndrome (e.g., alkaline phosphatase and bilirubin $> 5 \times$ upper limit of normal [ULN] associated with cholecystitis), only the diagnosis (e.g., cholecystitis) needs to be recorded on the Adverse Event electronic Case Report Form (eCRF).• Exacerbation of a chronic or intermittent preexisting condition, including either an increase in frequency and/or intensity of the condition• New conditions detected or diagnosed after study intervention administration, even though it may have been present before the start of the study• Signs, symptoms, or the clinical sequelae of a suspected drug drug interaction• Signs, symptoms, or the clinical sequelae of a suspected overdose of either study intervention or a concomitant medication. Overdose per se will not be reported as an AE/serious adverse event (SAE) unless it is an intentional overdose taken with possible suicidal/self harming intent. Such overdoses should be reported regardless of sequelae.• Lack of efficacy will not be reported as an AE or SAE. Such instances will be captured in the efficacy assessments. Nonetheless, the signs, symptoms, and/or clinical sequelae resulting from lack of efficacy will be reported as AEs or SAEs if they fulfill the definition of an AE or SAE.• The term "disease progression" or "progressive disease" should not be reported as an AE, rather, report the specific malignancy as the AE term.

Non-Serious Adverse Events of Special Interest (Immediately Reportable to the Sponsor)

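### The SAP's row for second primary cancers has no step to set aside the study tumour and, by its title, leaves out haematological cancers

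*SAP*

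**What the plan says.** SAP 3.8.3 states that the AESIs "will be summarized as below based on TEAEs" and then gives one search definition per event. For second cancers the whole definition is: "Secondary primary malignancies, based on SMQ “Non-haematological malignant tumours". It carries no exclusion, no condition that the tumour be new, no reference to histology and no link to the investigator's own AESI report. Other rows in the same list are refined: rhabdomyolysis is held to narrow-scope terms, and the ocular row leaves out named groups of terms.

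On display, SAP 3.8.3 says: "The AESIs will be summarized by group term, PT and highest CTCAE grade". SAP 3.8 adds that safety results are shown by cohort and overall. SAP 1 gives the population as patients with "recurrent or progressive melanoma or solid tumors with activating BRAF fusion or CRAF/RAF1 fusions or amplification".

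Protocol Appendix G lists second primary malignancies as an AESI without limiting the tumour type. On progression of the study tumour, the protocol says four things:

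- Appendix G, among events that are not adverse events: "expected progression, signs, or symptoms of the disease/disorder being studied, unless more severe than expected".
- Appendix G, among events that are adverse events, on the term for progression: it "should not be reported as an AE, rather, report the specific malignancy as the AE term".
- Section 8.1.6, on deaths in the adverse event reporting period, which are recorded as serious: "This includes death attributed to the progression of malignant disease". On the term to enter: "the event or condition that caused or contributed to the fatal outcome should be recorded as the single medical condition".
- Appendix G, definition of an SAE: death from progression is given as an example of something that cannot be an SAE, because it is not an adverse event in the first place.

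**The concern.** This row is the planned group-term summary of second cancers, and the protocol treats that outcome as worth looking for. Protocol 6.13 has skin lesions suspected of being keratoacanthoma or squamous cell carcinoma biopsied when they arise on treatment. Protocol 1.1.3 describes such lesions as common with Type-I BRAF inhibitors, attributes them to paradoxical activation, and says that DAY101 avoids that mechanism. A reader who wants to know whether this is borne out will look here.

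The search is by tumour type, and the study disease is of that same type in every patient. A count built that way can mix the disease under treatment with new cancers. A search restricted to non-haematological tumours also appears narrower than the event that the master protocol names.

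**Working it through.** No figure is stated for this AESI, so there is nothing to reproduce. The check is to follow each kind of event from the site's entry to the SAP row.

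1. **Expected, non-fatal progression.** Appendix G says this is not an adverse event. It does not reach the row.

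2. **Progression recorded as an adverse event**, for example because it is more severe than expected. Appendix G requires the name of the malignancy as the term. In this population that is melanoma or another solid tumour, which falls under the title of the search. The treatment-emergence filter does not remove it: SAP 3.1.6 admits new or worsening events, and the onset is after the first dose. The row counts it.

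3. **Death from progression in the reporting period.** Under 8.1.6 it is an SAE, entered under the condition that caused or contributed to death. If the site enters the tumour, the row counts it. If the site enters a complication, the row does not. Under the SAE definition in Appendix G there is no entry at all. The same death can thus give different counts according to the text followed.

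4. **New non-haematological primary.** The row counts it, as intended.

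5. **New primary melanoma in the melanoma cohort.** The row counts it, but the preferred term may be the same as in step 2. The preferred-term display may not show which is which.

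6. **New haematological primary.** By the title of the search it is outside the row. If treatment-emergent, it still appears in the general tables of SAP 3.8.2.

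Steps 2 and 3 can put the study tumour into the group-term count. Step 5 shows that a term-level exclusion would not be a safe remedy. Step 6 is the gap in scope.

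On size: one study-tumour entry adds 1/n to the group-term proportion, where n is the number of patients in the cohort. The cohort sizes in SAP Table 1 are redacted, and the documents give no rate of study-tumour entries or of second cancers. The effect cannot be put into figures.

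**The case against.** The strongest reply is that the row is descriptive and open to checking. It is shown by preferred term and by cohort. SAP 3.8.1 lists all adverse events by patient, and SAP 3.5.2 lists malignancy history. Protocol 8.2.2 gives each SAE a second assessment by the sponsor's safety physician. Expected progression is not an adverse event, and a fatal case may be entered under a complication. Most of this stands, and it keeps the severity low. It does not supply a rule for the group-term count, and in the melanoma cohort the preferred term may not settle the matter.

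On scope, the term list of the search is not in the documents, so the haematological gap is read from its title. The SAP also rests on sub-protocol 102a, which is not available. The SAP's AESI list has an item on growth velocity that the master list lacks, so the master list is not its only source. Both caveats stand. The skin-cancer rationale in the protocol supports the study-tumour part of this point, not the haematological part.

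Three stronger readings are tempting, and the documents do not support them:

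- A reader might infer that late second cancers are a special fault of this row, because treatment-emergent status ends 30 days after the last dose or at subsequent therapy. That limit applies to every AESI row, and later drug-related AESIs remain in the listings of SAP 3.8.1.
- A reader might infer that SAP 3.8.2 leaves open whether its SAE tables go beyond treatment-emergent events. SAP 3.1.6 and 3.8.1 base all adverse event analyses on treatment emergence.
- A reader might take a ceiling from protocol Table 2, which lists events in at least 10% of 99 patients and shows no malignancy term, so that any one term occurred in at most 9. That bounds single terms, not a group count, and the recording rules of that study are not given.

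**Conclusion.** The point holds in a limited form. Followed as written, SAP 3.8.3 can count the study tumour as a second primary cancer and, by the title of its search, leaves haematological second cancers out of the row.

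A reader might go further and infer that the count will be inflated, or that haematological second cancers will go unreported. Neither follows. Inflation depends on how sites apply protocol texts that conflict, and treatment-emergent haematological cases remain in the general tables.

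The conclusion assumes that the search covers what its title says and that sub-protocol 102a does not define the AESI differently. The size cannot be derived. The effect is confined to one descriptive safety row with no test or decision rule attached, and the overall response rate is untouched. Severity is low.

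**What to change.** In SAP 3.8.3:

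- Search both haematological and non-haematological malignancy terms, after checking the AESI scope in sub-protocol 102a.
- Count in the row only events that medical review confirms as a new primary. The inputs are the recorded primary diagnosis and histology (protocol 6.3, SAP 3.5.2) and the AESI questionnaires already required by protocol 8.1.1. Do not exclude by preferred term alone, because that could discard a new primary melanoma.
- Show study-tumour entries on a separate line, so that nothing retrieved by the search disappears.

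Protocol 8.1.6 and Appendix G must also be reconciled on whether a death from progression is an SAE.

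The cost is SAP wording and a short medical review of the malignancy terms. No new data are needed.

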##### **3.1.2. Reporting of Numerical Values**

Relevant descriptive statistics (n, mean, standard deviation, median, minimum, and maximum) will be calculated for continuous variables. Confidence intervals (CIs) will be provided where appropriate.

Frequencies and percentages will be presented for categorical and ordinal variables, with the frequencies reported as integers and percentages reported with one decimal place. Unless otherwise specified, the percentages will be calculated based on the total number of patients included for the analysis group. Frequencies and percentages for patients with missing data may be presented.

Means, medians, and confidence intervals will be reported to one decimal place more than the data reported on the case report form (CRF) or by the laboratory/vendor. Standard deviations will be reported to two decimal places more than the data.

A month is operationally defined to be 30.4375 days. Six months is operationally defined to be 182.625 days. One year is defined to be 365.25 days.

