### **3.2.2. Safety Analysis Set**

All patients enrolled in the study who receive at least one dose of tovorafenib will be included in the Safety Analysis Set.

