#### **3.3.3.4. Height and bone age**

Height and bone age will be collected for patients 12 – 18 years (inclusive). Patients without epiphyseal closure at the time of screening will have a bone age left wrist radiograph performed [REDACTED].

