## **3.8. Safety Analysis**

Safety will be evaluated by monitoring all adverse events, serious adverse events, adverse events of special interest, and abnormalities identified through physical examinations, vital signs, and laboratory assessments. Such events will be graded using the National Cancer Institute Common Terminology Criteria for Adverse Events, Version 5.0 (NCI CTCAE v5.0). All verbatim adverse event terms occurring on or after first study treatment will be mapped to Medical Dictionary for Regulatory Activities (MedDRA), and adverse event severity will be graded according to NCI CTCAE v5.0. All safety analyses will be performed with the Safety Analysis Set and presented by cohort and overall.

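### The growth-velocity AESI has no at-risk denominator, so its all-treated percentage understates the rate in patients still growing, by a factor the documents do not fix

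*SAP*

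**What the plan says.** **Event.** SAP 3.8.3 gives the item as "Decreased growth velocity, based on PT", then six preferred terms with no restriction by age or growth-plate status. The layout is fixed by "The AESIs will be summarized by group term, PT and highest CTCAE grade", so age does not enter the table.

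**Denominator.** SAP 3.8 states "All safety analyses will be performed with the Safety Analysis Set and presented by cohort and overall". SAP 3.2.2 defines that set: "All patients enrolled in the study who receive at least one dose of tovorafenib will be included in the Safety Analysis Set". SAP 3.1.2 adds "Unless otherwise specified, the percentages will be calculated based on the total number of patients included for the analysis group", and SAP 3.8.3 specifies nothing else. The subgroups in SAP 3.2.4 are sex and CNS tumor, and they apply to key efficacy endpoints only.

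**Who is measured.** SAP 3.3.3.4 says "Height and bone age will be collected for patients" aged 12 to 18 inclusive, with repeat wrist radiographs only where the epiphyses were open at screening. Protocol 6.15 uses the same age band and gives the risk of growth retardation as the reason for the repeat radiographs. Footnote c to SAP Table 2 limits height at later examinations to ages 12 to under 18.

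**What is analysed.** SAP 3.8.1 to 3.8.6 contain no analysis of height or bone age. SAP 3.5.1 tabulates age group (12 to under 18; 18 and over) and lists demographics by patient. SAP 3.8.1 lists all AEs by patient.

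**AESI lists.** The list in Protocol Appendix G, introduced by "Adverse events of special interest for this study include the following", has five items and no growth item. SAP 3.8.3 has six.

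**The concern.** A percentage is useful when everyone in its denominator could have had the event and would have been found to have it. Here neither condition is ensured. Patients who have finished growing cannot have slowed growth, and adults have no scheduled follow-up height that would reveal it. They still enter the denominator, so the printed percentage falls as the share of adults rises, whatever the drug does to growth.

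This is the one AESI in the list whose risk is confined to patients still growing. The interim and primary analyses have been dropped after early termination (SAP 2.2.1), so the final analysis is where the figure will appear. A reader who takes the tabulated percentage as the risk for an adolescent would read it too low.

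**Working it through.** The documents print no rate for this event, no adolescent count, and a redacted sample size, so there is no planned figure to reproduce. The check is algebra plus labelled assumptions.

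**Inputs from the documents:** denominator = all treated patients (SAP 3.1.2, 3.2.2, 3.8); no exception for this event (SAP 3.8.3); no age subgroup for safety (SAP 3.2.4).

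**Inputs assumed:** N = number treated; m = number of treated patients still growing; f = m/N; x = patients with the event, all among the m.

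**Step 1. The factor.** The reported rate is x/N and the rate in growing patients is x/m. Their ratio is (x/m)/(x/N) = N/m = 1/f. It does not depend on x.

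**Step 2. Range.**

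| f (assumed) | factor 1/f | a true 20% would print as 20% × f |
|---|---|---|
| 75% | 1.33 | 15.0% |
| 50% | 2 | 10.0% |
| 33% | 3 | 6.7% |
| 25% | 4 | 5.0% |
| 20% | 5 | 4.0% |
| 10% | 10 | 2.0% |
| 5% | 20 | 1.0% |

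The factor reaches 3 only when growing patients are about one third or less of those treated, and 5 only at 20% or less.

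**Step 3. Counts, for illustration.** Take N = 40 and one event.
- m = 4: 1/40 = 2.5% (exact 95% CI 0.1 to 13.2) against 1/4 = 25.0% (0.6 to 80.6); factor 40/4 = 10.
- m = 20: 1/40 = 2.5% against 1/20 = 5.0% (0.1 to 24.9); factor 40/20 = 2.

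The SAP plans no intervals for AESIs. They are shown only to make clear how little a rate on four patients can establish.

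**Step 4. Events outside the growing group.** The term *Body height decreased* can be coded in an adult. If y such patients are counted, the reported rate is (x + y)/N and the factor becomes (1/f) × x/(x + y). With N = 40, m = 4, x = 1, y = 1, that is 25.0% against 2/40 = 5.0%, a factor of 10 × 1/2 = 5. The dilution looks smaller, but the table is then mixing adult height loss with slowed growth. A restricted rate therefore needs the same restriction above and below the line.

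**Step 5. By cohort.** The cohorts are not defined by age (SAP 2.2), so f may differ between them. In a cohort with no growing patients, the percentage is 0 by construction unless an adult event is coded.

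**The case against.** **The size is unknown.** A reader might infer that the treated patients are mostly adults and the dilution several-fold. The documents support neither as fact: they give an age floor of 12, two cohorts not defined by age, and a redacted Table 1. This part of the objection stands in full.

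**Adults can be coded with the event.** It is tempting to say that adults cannot have it. That is true of slowed growth, but not of the event as defined, because *Body height decreased* and *Body height abnormal* carry no age limit. This stands.

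**Height findings can reach the AE data.** SAP 3.3.3 has clinically significant abnormalities in safety assessments reported as AEs, and Protocol 6.15 compares height with growth curves. So serial height is not ignored. What remains is that a slowing not judged clinically significant would appear in no planned summary. SAP 3.1.5 provides in general terms for listing results, but no height change from baseline is planned.

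**Little is hidden.** The all-treated percentage is correct for what it claims to be and follows one uniform rule. Age-group counts and patient listings let a reader rebuild an approximate rate for those under 18. This limits the harm, but the rebuilt rate cannot separate open from closed epiphyses, because the tabulated counts do not give that status.

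**The AESI lists.** A reader might call five items against six an error. The SAP also rests on the DAY101-102a sub-protocol (SAP 1), which is not among the documents supplied and may list the item. The difference is only something to reconcile.

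**Conclusion.** The concern holds as a fault of presentation in SAP 3.8.3. Decreased growth velocity is reported over all treated patients, with no at-risk denominator and no age split. The rate in growing patients is therefore understated by exactly 1/f, provided all events fall in that group. Some understatement occurs whenever any treated patient has finished growing. Its size cannot be stated: 2 at f = 50%, 3 at 33%, 5 at 20% and 10 at 10% are illustrations, not estimates.

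A stronger reading, that the table will make a common adolescent harm look rare, would need both a small f and a high event rate, and the documents give neither. No data are lost and the primary endpoint is untouched. The change is still worth making because it is cheap and corrects the one safety rate whose risk group is a defined subset of the patients.

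**What to change.** 1. In SAP 3.8.3, keep the all-treated figure and add n/N for this AESI, with **both** numerator and denominator restricted to treated patients without epiphyseal closure at screening. Where that status is missing, use age 12 to under 18. Show the counts, not a percentage alone.
2. Add a listing, for the same patients, of height change from baseline and bone age, from data already collected.
3. Before setting the flag, reconcile the age limits for height follow-up: 12 to under 18 in footnote c to SAP Table 2, against 12 to 18 inclusive in Protocol 6.15 and SAP 3.3.3.4. As written, an 18-year-old with open epiphyses could enter the listing without scheduled follow-up height.
4. Check the AESI lists in Protocol Appendix G and SAP 3.8.3 against the sub-protocol, and record the reason for any difference.

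Cost: one flag and one listing. The added rate will rest on few patients and be imprecise.
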